	4.3.1 Inclusion Criteria		
4.0	Protocol Summary, Exclusion Criteria; 4.3.2 Exclusion Criteria	Exclusion criterion #11 was updated to clarify, "Has had any prior or current prostate cancer therapy, including: a) Biologic therapy for prostate cancer b) Chemotherapy for prostate cancer c) Hormonal therapy for prostate cancer within three months of procedure d) Radiotherapy for prostate cancer e) Surgery for prostate cancer."	Clarifies that all prior or current prostate cancer therapies are exclusionary.
4.0	Protocol Summary, Exclusion Criteria; 4.3.2 Exclusion Criteria	Exclusion criterion #15 was updated to clarify, "Is actively bleeding, has a bleeding disorder, or is unable to interrupt blood thinning medications as clinically indicated per pre-operative best practices. "	Clarifies that patients who are on blood thinning medications but can interrupt them prior to treatment will not be excluded.
4.0	Protocol Summary, Exclusion Criteria; 4.3.2 Exclusion Criteria	Exclusion criterion #16 was updated to clarify, "Is a member of a vulnerable population, such as cognitively impaired or incarcerated, that could expose them to undue influence, coercion, or inability to obtain informed consent. "	Updated to add more inclusive language.
4.0	Protocol Summary, Study Procedure; 4.2 Informed Consent; 4.3 Eligibility Criteria	Updated to define enrollment to occur at time of informed consent.	Administrative change.
4.0	3.2.2 Disease Localization: Transperineal or Transrectal Prostate Biopsies; Table 4-4 Schedule of Subject Evaluations	Updated to allow enrollment PSA to be taken after enrollment biopsy as long as it is taken greater than 30 days after biopsy.	Updated so as not to require patients to be re-biopsied if enrollment PSA is older than 180 days and needs to be reassessed.
4.0	4.4 Baseline	Updated to clarify that Screening and Baseline visits may be combined.	Administrative change.
4.0	4.4 Baseline; 4.6.11 Quality of Life (QoL) Assessment Procedures; 4.6.12	Updated to allow 30 days between Baseline visit and IRE treatment.	Updated to account for scheduling of the NanoKnife procedure and to account for postponements in treatment.

	Physical Examination; Table 4-4 Schedule of Subject Evaluations		
4.0	4.5 Procedure Preparation	Updated assessments to be performed prior to procedure— previously urinalysis and blood draw had been included in error. Bowel preparation updated to remove 1-2 hour requirement to conform with standard practice.	Administrative change.

2.0 Change History

Version/Date	Change Log
0.1/13-Dec-2021	Initial draft to AngioDynamics
0.2/08-Feb-2022	
Updated after AngioDynamics review:
 
 Section 9 renamed to “Endpoints” instead of “Endpoints and Covariates”. “Missing Data” section clarified. “Demographic and Baseline Characteristics” section clarified. Coding dictionaries versions updated. All protocol deviations will be presented, instead of just important protocol deviations. Transrectal ultrasound will not be presented. Additional NanoKnife procedure information will now be presented in tables, not only listings. Gleason scores for patients that do have a positive biopsy added for both negative in-field biopsy tables. Paired t-test added for urinary and erectile function change from baseline assessments. Screening versus Baseline clarifications, Nadir definition added. Adverse events versus adverse device events clarification. Adverse event relationship to NanoKnife system procedure categories updated. Physical examination analysis description updated.
1.0/23-Mar-2022	
Updated after AngioDynamics review of version 0.2:
 
 CRF version 8.0 dated 10Feb2022 included. Agreed on the statement regarding multiple imputation within Section 6.1 Changes from Protocol. Agreed on to remain Prostate volume within section 8.0 Study Design. “Re-treatment with IRE or first re-treatment with other type” information was included in SAP and TFLs where needed. 95% CI decimal places was included in section 12.0 Statistical Methods. Section 12.2 was renamed to “Demographics”. MedDRA and WHO-Drug versions have been included. Subgroup analysis have been added in Section 12.7 Efficacy Analyses For the section and subsections 12.7.3 Assessment of Urinary Function, change from baseline is included for all timepoints (modified from the Protocol) EPE and seminal vesicle invasion is excluded from section 12.7.7 Assessment of Ablation Effectiveness by Evaluation of Prostate Tissue by mpMRI, and tables. The definition for cancer-bearing prostate tissue lesions is included. In section 12.7.8 Assessment of Need for Secondary or Adjuvant Treatment Following Treatment with the NanoKnife System, options “in-field or out-of-field” have been added to “positive unscheduled biopsy”. TFLs have been also updated. Section 12.8 Safety Analyses have been updated with clarity for re-treatment of lesions.

	
 Section 10.2 Adverse Events changing in severity/relationship with the treatment is created. In section 12.8.3 Laboratory Data text have been modified to state that results will be categorical (normal, abnormal and not clinically significant, or abnormal and clinically significant). Laboratory tests have been specified. Shift tables for urinalysis will be based on worst-case post-baseline value.
1.1/11-Apr-22 (SPONSOR & ICON APPROVED)	
 In section 12.6 NanoKnife System Procedure, inclusion of “and device malfunctions (i.e., were there any device malfunctions or error messages during the procedure?)” In section 12.7.10 Sensitivity Analysis, inclusion of a sensitivity analysis. In Table 17, update laboratory tests and SI units, In section 12.8.4 Vital Signs, adding BMI.
1.2/10-Mar-2023	
 Imputation of Missing or Partial Dates Updates after Protocol amendment – Protocol version 4.0 (date 20-Jan-2023) and CRF version 10.0 (date 14-Feb-2023): Inclusion/Exclusion criteria; possibility for combination of Screening and Baseline visit; Allow post-procedure visit to be conducted over the phone (if no urinalysis/MRI are needed)
2.0/06-Jun-2023 (SPONSOR & ICON APPROVED)	
 Approved version after AngioDynamics’ review of v 1.2

4.0 Purpose

The Statistical Analysis Plan (SAP) describes the statistical methods to be used during the reporting and analyses of data collected under AngioDynamics, Protocol 2021-ONC-01.

5.0 Scope

The Statistical Analysis Plan outlines the following:

- Study Objectives
- Study Design
- Applicable Study Definitions
- Statistical Methods

6.0 Introduction

This SAP should be read in conjunction with the study protocol and case report forms (CRFs). Any further changes to the protocol or CRFs may necessitate updates to the SAP. This version of the plan has been developed using the protocol version 4.0 dated 20-Jan-2023 and CRF version 10.0 dated 14-Feb-2023.

This is a prospective study, with no blinding mechanism. A final version of the SAP will be issued for sponsor approval prior to database lock.

6.1 Changes from Protocol

There are no plans to further the follow-up beyond the 12 months. The continuation of follow-up for up to 5 years, as standard of care, to assess the rate of progression, re-intervention, and adverse events is not expected at this point. This exploratory endpoint stated in protocol is outside of the scope of this SAP.

No multiple imputation will be used for the missing items for 15-Item International Index of Erectile Function (IIEF-5), International Prostate Symptom Scores (IPSS), and Expanded Prostate Cancer Index Composite (EPIC) questionnaires, as stated in the protocol.

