6.4 Missing Data

The following imputation methods will be used for the primary analysis of all endpoints:

- When calculating the proportion of subjects with a negative in-field biopsy, subjects with missing biopsy information post-ablation will be imputed as “positive”
- Subjects with missing pre- or post-ablation prostate volume measurements will be imputed as having a zero change in volume
- Missing PSA data will be imputed using last observation carried forward (LOCF)
- Missing data for IIEF-5, IPSS and EPIC questionnaires will be imputed using a multiple imputation approach at the item/question level.

All other endpoints/data (e.g., safety events) will be analyzed based on available (non-imputed) data, unless specified otherwise.

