12.7.3 Assessment of Urinary Function

Urinary function is assessed by comparison of pre- and post-operative UCLA-EPIC Urinary Domain ([Wei et al., 2000](#)), IPSS ([Barry et al., 1992](#)), and IPSS-QoL scores ([Rees, 2013](#)).

Summary statistics will be presented for the timepoints where the questionnaires are collected (baseline, 1, 3, 6, 9, and 12 month follow-up). Additionally, all the follow-up changes from baseline will also be presented, along with the associated paired t-test value.

² Note: Subjects with early positive out-of-field biopsies will not be considered failures for the primary efficacy endpoint.

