12.7.3.2 IPSS

For the purpose of assessing the urinary function, the IPSS will be used. It consists of 8 questions, the first 7 related to severity of a range of urinary symptoms (three storage symptoms [urgency, frequency and nocturia] and four voiding symptoms [weak stream, hesitancy, intermittency and straining]) – scoring from 1 to 5 for each question to make a maximum total score of 35. Questions are detailed in [Table 9](#), along with correspondent answers and respective item response value.

Table 9 IPSS questions

Question	Possible answers	Item Response Value
1.Over the past month, how often have you had a sensation of not emptying your bladder completely after you finished urinating?	Not at all Less than 1 time in 5 Less than half the time About half the time More than half the time Almost always	0 1 2 3 4 5
2.Over the past month, how often have you had to urinate again less than 2 hours after you finished urinating?	Not at all Less than 1 time in 5 Less than half the time About half the time More than half the time Almost always	0 1 2 3 4 5
3.Over the past month, how often have you found that you stopped and started again several times when you urinated?	Not at all Less than 1 time in 5 Less than half the time About half the time More than half the time Almost always	0 1 2 3 4 5
4.Over the past month, how often have you found it difficult to postpone urination?	Not at all Less than 1 time in 5 Less than half the time About half the time More than half the time Almost always	0 1 2 3 4 5
5.Over the past month, how often have you had a weak stream?	Not at all Less than 1 time in 5 Less than half the time About half the time More than half the time Almost always	0 1 2 3 4 5
6.Over the past month, how often have you had to push or strain to begin urination?	Not at all Less than 1 time in 5 Less than half the time About half the time More than half the time	0 1 2 3 4

Question	Possible answers	Item Response Value
	Almost always	5
7. Over the past month or so, how many times did you get up to urinate from the time you went to bed until the time you got up in the morning?	None	0
	1 time	1
	2 times	2
	3 times	3
	4 times	4
	5 or more times	5

The total score will be the sum of all item scores. The total symptom score will be stratified as Mild (total score between 0 and 7), Moderate (from 8 to 19), and Severe (from 20 to 35). All items must be completed, no missing items are acceptable ([Barry et al., 1992](#)).

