12.7.4 Assessment of Erectile Function

For the purpose of assessing erectile function, the IIEF-15 questionnaire will be used. Summary statistics will be presented for the timepoints where the questionnaires are collected (baseline, 1, 3, 6, 9, and 12 month follow-up). Additionally, all the follow-up changes from baseline will also be presented, along with the associated paired t-test value.

The questionnaire consists of 15 questions, where 6 are related to erectile function, 3 refer to satisfaction with intercourse, 2 are related to orgasmic function, 2 refer to sexual desire, and 2 refer to overall sexual satisfaction.

The items are not weighted and total scores range from 5 to 75. The domain scores are computed by summing the scores for each individual item in each domain. The subscales range as follows: Erectile Function (1-30), Intercourse Satisfaction (0-15), Orgasmic Function (0-10), Sexual Desire (2-10), and Overall Sexual Satisfaction (2-10). On the Erectile Function subscale, lower scores indicate worse erectile

dysfunction, while on the remaining subscales, higher scores indicate less dysfunction. The overall score considers all questions. All items must be completed, no missing values are acceptable ([Rosen et al., 2002](#)).

For the Erectile Function subscale, the following questions are considered ([Table 11](#)):

Table 11 Erectile Function subscale questions

Question	Possible answers	Item Response Value
Over the last four weeks, how often were you able to get an erection during sexual activity?	No sexual activity Almost never or never A few times (less than half the time) Sometimes (about half the time) Most times (more than half the time) Almost always or always	0 1 2 3 4 5
Over the last four weeks, when you had erections with sexual stimulation, how often were your erections hard enough for penetration?	No sexual activity Almost never or never A few times (less than half the time) Sometimes (about half the time) Most times (more than half the time) Almost always or always	0 1 2 3 4 5
Over the last four weeks, when you attempted intercourse, how often were you able to penetrate (enter) your partner?	No sexual activity Almost never or never A few times (less than half the time) Sometimes (about half the time) Most times (more than half the time) Almost always or always	0 1 2 3 4 5

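### The SAP withdraws the protocol's item-level multiple imputation for IPSS, IIEF-15 and EPIC without a reason, leaving strict scoring rules and visit-by-visit paired t-tests on available pairs

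*Combined protocol and SAP*

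**What the plan says.** Protocol 6.4 opens its list of rules with "The following imputation methods will be used for the primary analysis of all endpoints". One rule is "Missing data for IIEF-5, IPSS and EPIC questionnaires will be imputed using a multiple imputation approach at the item/question level". The others cover biopsy, prostate volume and PSA.

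SAP 6.1, under changes from the protocol, states "No multiple imputation will be used for the missing items" of the same three instruments. SAP 10.6 carries over the biopsy, volume and PSA rules and lists no questionnaire rule, so available data are used.

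Scoring then decides what counts as available:

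- **IPSS** (SAP 12.7.3.2): "All items must be completed, no missing items are acceptable".
- **IIEF-15** (SAP 12.7.4): "All items must be completed, no missing values are acceptable". Protocol Appendix E 2.1.2 says that a blank item makes its own subscale missing.
- **EPIC** (SAP 12.7.3.1): the urinary domain needs 10 of 12 items; the Incontinence subscale needs 4 of 4.

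SAP 12.7.3 presents change from baseline at every follow-up visit "along with the associated paired t-test value"; SAP 12.7.4 does the same for IIEF-15. SAP 12.7.10 repeats the efficacy analyses in the per-protocol population. Its only missing-data sensitivity analysis concerns the biopsy endpoint.

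**The concern.** Two documents in force disagree on a prespecified primary method. The SAP change log records only that the statement on multiple imputation was agreed at version 1.0 (23-Mar-2022). Protocol 4.0 (20-Jan-2023) is later and still contains the imputation rule, and SAP 2.0 (06-Jun-2023) is written against that protocol. The SAP 6.1 sentence also closes with a reference to the protocol that can be misread as saying that the protocol ruled imputation out.

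Item-level imputation offsets strict scoring rules. The SAP keeps the strict rules for IPSS and IIEF-15 and removes the offset. A paired t-test needs a computable score at baseline and at the visit in question, so each visit may rest on a different subset of men. The mean change is then unbiased only if a missing pair is unrelated to the change itself, and no planned analysis tests that.

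Urinary and erectile function are the first-listed secondary objective. Protocol 3.2 also counts the effect on urologic function as part of the safety assessment, and Table 8-1 lists erectile dysfunction and incontinence as possible device effects. If men with worse function answer less completely, the reported change will look too favourable.

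**Working it through.** **Inputs from the documents.** IPSS has 7 symptom items. IIEF-15 has 15 items, 6 of them in Erectile Function. The EPIC urinary domain needs 10 of 12 items and Incontinence 4 of 4. Protocol 6.2 gives 100 subjects, 15% drop-out and 118 enrolled.

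**Plan's own figure.** 100 / (1 − 0.15) = 117.6, rounded up to 118. It reproduces. It is the only stated figure that bears on how many questionnaires will be available.

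**Input not in the documents.** The item non-response rate q. I assume 1%, 2% and 3%, independent between items and between visits.

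**Formulas.** If all k items are required, a score is computable at one visit with probability (1 − q)^k and at both visits with probability (1 − q)^(2k). Pairs lost = 1 − (1 − q)^(2k). For the EPIC domain, the chance of at least 10 of 12 answers is squared.

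| Score | Pairs lost | q = 1% | q = 2% | q = 3% |
|---|---|---|---|---|
| IIEF Erectile Function | 1 − (1 − q)^12 | 11% | 22% | 31% |
| IPSS total | 1 − (1 − q)^14 | 13% | 25% | 35% |
| IIEF-15 total | 1 − (1 − q)^30 | 26% | 45% | 60% |
| EPIC Incontinence | 1 − (1 − q)^8 | 8% | 15% | 22% |
| EPIC urinary domain | 1 − P(at least 10 of 12)² | below 0.1% | 0.3% | 1.0% |

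**Precision at q = 2%.** The standard error grows by 1/√(fraction kept): 1/√0.785 = 1.13 for Erectile Function, 1/√0.754 = 1.15 for IPSS and 1/√0.545 = 1.35 for the IIEF-15 total.

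**Other end of the range.** Independence is close to the worst case. If a 2% rate arose entirely from wholly blank forms, independently at each visit, the loss would be 1 − 0.98² = 4% of pairs for every score.

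**Bias, by simulation on assumed inputs.** Change SD of 8 points; correlation of 0.5 to 0.7 between earlier and 12-month change; odds of missing multiplied by 1.5 to 2 per SD of worse earlier change. The available-pairs mean is then too favourable by about 0.25 to 0.55 points at 15% missing, 0.5 to 1.05 at 30% and 0.7 to 1.6 at 45%. If missingness is unrelated to outcome, the bias is about zero.

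**The case against.** The best reply is that the withdrawal is declared and falls back on the instruments' own scoring rules. For EPIC and IIEF-15 those rules already stand in the protocol's Appendix E. Missing data are also pursued (SAP 10.6, protocol 7.3), and IIEF items 1 to 10 have a zero category, so sexual inactivity need not leave a blank. Protocol 6.2 says the study is not powered for claims on secondary endpoints. All of this limits the consequence. It does not supply a reason for dropping the protocol's primary method, or a check on the result.

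Several stronger readings are not supported:

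- *That much of the IIEF-15 and IPSS data will be discarded.* No non-response rate is given. The loss is large only for the 15-item total at about 2% or more.
- *That one blank voids the whole IIEF-15 form.* SAP 12.7.4 is unclear; the protocol appendix voids only the affected subscale.
- *That only completers are analysed.* A man who misses one follow-up visit still counts at the others.
- *That the t-test displaced a protocol model.* Protocol 6.9 only tabulates change; the SAP added the test.
- *That men who leave after re-treatment are lost because imputation was dropped.* Excluding data after re-treatment with another modality is a protocol rule (4.6.16, 6.9), and item-level imputation would not bring those visits back.

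**Conclusion.** The concern holds as a conflict between protocol 6.4 and SAP 6.1 on a primary missing-data method. The SAP version carries a possible loss of precision and a possible bias in secondary endpoints. The exposure is mainly in IPSS, IIEF-15 and EPIC Incontinence.

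The size is conditional. At an assumed 2% independent item non-response, Erectile Function loses about 22% of pairs, IPSS 25% and the IIEF-15 total 45%; clustering would reduce all three. The direction and size of any bias depend on why items are blank, which the documents cannot settle. A reader might infer that harm will be hidden, but the documents establish only that the plan could not detect it if it were. Adverse events are collected separately, and the primary biopsy result is not affected.

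**What to change.** 1. Restore item-level multiple imputation for IPSS, IIEF-15 and EPIC as the main analysis, in line with protocol 6.4. Reword SAP 6.1 so that it cannot be read as the protocol excluding imputation, and correct IIEF-5 to IIEF-15 in both documents.
2. State in SAP 12.7.4 that, for observed-case scoring, a blank IIEF item voids its own subscale and the total, not the other subscales.
3. Estimate change at each visit from one repeated-measures mixed model per score, using all observed visits, with baseline as a response. Say whether wholly missing forms are imputed or left to the model.
4. Keep the observed-case paired t-test as a sensitivity analysis, and report the number of computable scores and pairs per visit.

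The cost is SAP wording and programming; no new data are needed, and SAP 6.0 foresees a final version before database lock. The downside is reliance on data missing at random, although the available-pairs analysis needs the stronger condition that missingness is unrelated to outcome. For men whose data are excluded after re-treatment, the model estimates scores as if re-treatment had not occurred, and the SAP should say so.

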7.0 Study Objectives

7.1 Primary Study Objectives

- To determine the NanoKnife System's ablation effectiveness by measuring the negative in-field biopsy rate at 12 months.
- To determine the NanoKnife System's procedural and post-procedural safety profile by evaluating adverse event incidence, type, and severity through 12 months.

7.2 Secondary Study Objectives

- To evaluate urinary and erectile function after NanoKnife System treatment using validated subject questionnaires (University of California Los Angeles-EPIC[UCLA-EPIC] Urinary Domain [[Wei et al., 2000](#)], IPSS [[Barry et al., 1992](#)], and IPSS quality of life [IPSS-QoL] [[Rees, 2013](#)], IIEF-15 [[Rosen et al., 2002](#)]).
- To determine post-NanoKnife System treatment prostate-specific antigen (PSA) kinetics, including time to PSA nadir and post-nadir PSA stability.
- To determine the change in prostate volume by comparison of prostate volume measured on multiparametric magnetic resonance imaging (mpMRI) pre-treatment and at 12 months post-treatment.

- To determine the effectiveness of therapy by assessing the need for secondary or adjuvant treatment following therapy.
- To determine health-related quality of life (HRQoL) levels after treatment with the NanoKnife System using a validated subject questionnaire – 5-dimension scale EuroQoL (EQ-5D) ([Oppe et al., 2014](#)).

8.0 Study Design

This is a prospective, non-randomized pilot study in 118 subjects treated at up to 20 clinical sites in the United States. The schedule of data collection is summarized below ([Table 1](#)).

This study will involve 118 subjects who meet the intermediate-risk criteria defined by this protocol. The biopsy and imaging techniques that will adopt within this trial are mpMRI and transperineal or transrectal prostate biopsy (fusion targeted biopsy of lesion plus 10-14 core systematic biopsies to include adequate sampling of peripheral zone). The subjects' prostate lesions, the locations of which will be determined by ultrasound-guided transperineal or transrectal prostate biopsy, will be targeted for treatment with the NanoKnife System. The primary objective of this the study will be to evaluate the NanoKnife System's ablation effectiveness by measuring the negative in-field biopsy rate at 12 months, and the procedural and post-treatment safety of the NanoKnife System via incidence and severity of adverse events through 12 months. The secondary objective of this study is to evaluate urinary and erectile function after NanoKnife System treatment using validated subject questionnaires, and to evaluate pre- and post-treatment changes in PSA and prostate volume. Other secondary outcomes include the effectiveness of the NanoKnife System by assessing the need for secondary or adjuvant treatment and health-related quality of life evaluated using validated subject questionnaires.

This group of subjects will be followed for safety and efficacy for 12 months. Safety will be assessed via incidence and severity of adverse events and evaluation of the treatment effect will be assessed via urologic function and quality of life. Local efficacy will be characterized via negative biopsy, post-treatment PSA kinetics including time to PSA nadir and post-nadir PSA stability, and changes in prostate volume.

Table 1 Data Collection

Study Assessment	Visit 1	Visit 2	Visit 3	Post-Procedure ¹⁰	Visit 4	Visit 5	Visit 6	Visit 7	Visit 8
	Screening	Baseline ³	NanoKnife Treatment		1 month 30 ± 7 days	3 months 90 ± 14 days	6 months 180 ± 14 days	9 months 270 ± 14 days	12 months 365 ± 28 days
Informed Consent ¹	X								
Enrollment	X								
Medical History	X								
Standard Physical Exam		X			X	X	X	X	X
Abbreviated Physical Exam			X						
Vitals Assessment ⁴		X	X		X	X	X	X	X
CBC Panel		X							
Prothrombin Test (PT)		X							
Partial Thromboplastin Time (PTT)		X							
Urinalysis		X	X ⁹	X ⁵	X ⁵	X ⁵	X ⁵	X ⁵	X ⁵
Transrectal US	X		X						X
MRI protocols	X ²			X ⁶		X			X
Biopsy ^{7,8}	X ²								X
PSA	X ²				X	X	X	X	X
UCLA-EPIC Urinary Questionnaire		X			X	X	X	X	X
IPSS & IPSS-QoL Questionnaire		X			X	X	X	X	X
IIEF-15 Potency Questionnaire		X			X	X	X	X	X
EQ-5D Questionnaire		X			X	X	X	X	X
NanoKnife System Procedure			X						
Concomitant Medications		X	X	X	X	X	X	X	X
Adverse Event Assessment			X	X	X	X	X	X	X

CBC = Complete blood count; EQ-5D = 5-Dimension scale EuroQoL; IIEF-15 = 15-Item international index of erectile function; IPSS = International prostate symptom scores; PSA = Prostate-Specific Antigen; QoL = Quality of life; UCLA-EPIC = UCLA expanded prostate cancer index composite; US = Ultrasound.

1. Must be signed and dated prior to completing any study procedures.
2. Must be completed within 180 days prior to enrollment in the study. Prostate-specific antigen for enrollment must be completed prior to biopsy, or must be taken more than 30 days after biopsy.
3. Complete within 30 days prior to NanoKnife System treatment.
4. Vitals assessments include height and weight, temperature, blood pressure, respiration rate and pulse. Note, height only needs to be collected at Baseline.
5. Complete only if there is a question of an active urinary tract infection.
6. Complete only if clinically indicated (i.e., the subject is experiencing unexpected adverse events following treatment).
7. Transperineal or Transrectal Prostate Biopsy (template mapping and/or limited targeted).
8. Complete at additional time points if subject has a lesion \geq Prostate Imaging – Reporting and Data System 3 on the 3-month magnetic resonance imaging, experiences biochemical failure as defined by the Phoenix criteria as nadir + 2 ng/mL, or upon clinical suspicion.
9. Complete pre-treatment, and at discharge only if there is a question of an active UTI.
10. Complete within 3 to 10 days of NanoKnife System treatment. This visit can be conducted over the phone, as long as urinalysis and MRI are not clinically indicated.

